6.1 Determination of Sample Size

There was no formal sample size calculation carried out for this clinical observational study because the study was not planned to test any formal hypothesis. Prior to the study commencement, it was planned to enroll 30 subjects into the study, and the sample size was accrued. However, a total of 3 subjects were excluded from all analyses for having met protocol deviations.

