7.1 General

Smith & Nephew's Global Biostatistics group will conduct the statistical analysis for this study. Unless otherwise stated, all significance tests and hypothesis testing will be two-sided, performed at the 5% significance level. Resulting p-values will be quoted and 95% two-sided confidence intervals will be generated where appropriate. All p-values will be rounded to three decimal places, p-values less than 0.001 will be presented as '<0.001' in all tables.

Where data summaries are specified, categorical and ordinal variables will be summarized with frequencies and percentages. Continuous variables will be summarized with the following summary

CONFIDENTIAL AND PROPRIETARY

This document contains information that is confidential and proprietary to Smith & Nephew PLC and Smith & Nephew, Inc. and is intended for use only by Smith & Nephew and its manufacturer. It shall not be reproduced or copied in whole or in part, nor shall the contents be disclosed by any means without prior written permission from Smith & Nephew, nor shall anyone make any use of it that is contrary to the expressed or implied wishes of Smith & Nephew

Statistical Analysis Plan	Smith+Nephew
A Prospective, Non-randomized, Multi-Center Investigation of All-suture-based Repair of Horizontal Meniscal Tears (STITCH Study)	Number: CTX-CP001
	Version: 1, 4-Sept-2019
	Page: 8 of 15

statistics: number of observations, mean, median, standard deviation, minimum and maximum values. All analyses will be performed in SAS 9.4 or later.

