7.3 Handling of Missing, Incomplete and Repeat Data

All data will be analyzed as observed cases unless otherwise indicated

CONFIDENTIAL AND PROPRIETARY

This document contains information that is confidential and proprietary to Smith & Nephew PLC and Smith & Nephew, Inc. and is intended for use only by Smith & Nephew and its manufacturer. It shall not be reproduced or copied in whole or in part, nor shall the contents be disclosed by any means without prior written permission from Smith & Nephew, nor shall anyone make any use of it that is contrary to the expressed or implied wishes of Smith & Nephew

Statistical Analysis Plan	Smith+Nephew
A Prospective, Non-randomized, Multi-Center Investigation of All-suture-based Repair of Horizontal Meniscal Tears (STITCH Study)	Number: CTX-CP001
	Version: 1, 4-Sept-2019
	Page: 9 of 15

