7.4 Derived Data

The study visits for this study are:

Stud Visit 1 = Screening visit

Study Visit 2 = Procedure visit

Study Visit 3 = Day 7-15

Study Visit 4 = Day 90

Study Visit 5 = Day 185

Study Visit 6 = Day 365

Study Visit 7 = Day 730

Analysis Populations

- Indicator for inclusion in the safety population.
- Indicator for inclusion in the analysis population.

Study Duration (will be calculated for each subject):

Study duration [days] = Date of study discontinuation – date of initial surgery

Freedom from reoperation of the index meniscus repair site (will be calculated at each visit):

Proportion of subjects with freedom from reoperation of the index meniscus repair site

$$= \frac{\text{Number of subjects whose known status were without repair}}{\text{Total number of participants with known repair status}} * 100\%$$

Change from pre-operative to post-operative visits in patient reported outcomes:

Change from pre- to post-operative visit will be calculated as:

Post – operative value_{Study Visit n} – Pre – operative value_(Study Visit 1), where n = 4,5,6,

Time since injury:

Time since injury will be calculated as:

Time since injury (in wk) = (Date of surgery – Date of injury)/7

CONFIDENTIAL AND PROPRIETARY

This document contains information that is confidential and proprietary to Smith & Nephew PLC and Smith & Nephew, Inc. and is intended for use only by Smith & Nephew and its manufacturer. It shall not be reproduced or copied in whole or in part, nor shall the contents be disclosed by any means without prior written permission from Smith & Nephew, nor shall anyone make any use of it that is contrary to the expressed or implied wishes of Smith & Nephew

Statistical Analysis Plan	Smith+Nephew
A Prospective, Non-randomized, Multi-Center Investigation of All-suture-based Repair of Horizontal Meniscal Tears (STITCH Study)	Number: CTX-CP001
	Version: 1, 4-Sept-2019
	Page: 10 of 15

Time to re-operation:

Time to reoperation will be calculated as:

Time to re-operation (in wk) = (Date of re-operation surgery – Date of original surgery)/7

Minimal clinically important differences (MCIDs):

- MCID-IKDC (Day185) Indicator = 1 if IKDC difference from baseline to Day 185 > 6.3,
= 0 otherwise;
- MCID-IKDC (Day 365) Indicator = 1 if IKDC difference from baseline to Day 365 > 16.7,
= 0 otherwise;
- MCID-Lysholm (Day365) Indicator = 1 if Lysholm difference from baseline to Day 365 > 10.1,
= 0 otherwise;

Adverse Events

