The patient reported outcomes (IKDC, KOOS Pain, KOOS Symptom, KOOS ADL, KOOS Sport, KOOS QOL, Lysholm, Tegner) will be summarized at each visit using descriptive characteristics for continuous variables (i.e. mean, median, SD, minimum, and maximum values). In addition, changes from baseline (Study Visit 1) to the subsequent follow-up visits will be similarly summarized. Results will be presented in narrative and graphically.

These measures will also be analyzed using inferential statistics. As appropriate, a repeated measure ANOVA or Wilcoxon signed rank test will be completed for each outcome measure. If a significant trend is identified, significance among time points, especially preoperative measures, may be further explored using the appropriate pair-wise comparisons. In all cases a p value equal to or less than 0.05 will be considered significant. Ninety-five percent (95%) CIs will be presented as well as corresponding p-values from the pair-wise comparisons of means from baseline to planned visits of interest (i.e. from Study Visit 1 to Day 90, Day 185, Day 365, and Day 730).

In addition, for Lysholm and/or IKDC, the numbers and proportions of subjects (out of total number of subjects providing data), together with a 95% confidence interval (calculated using the Clopper-

CONFIDENTIAL AND PROPRIETARY

This document contains information that is confidential and proprietary to Smith & Nephew PLC and Smith & Nephew, Inc. and is intended for use only by Smith & Nephew and its manufacturer. It shall not be reproduced or copied in whole or in part, nor shall the contents be disclosed by any means without prior written permission from Smith & Nephew, nor shall anyone make any use of it that is contrary to the expressed or implied wishes of Smith & Nephew

Statistical Analysis Plan	Smith+Nephew
A Prospective, Non-randomized, Multi-Center Investigation of All-suture-based Repair of Horizontal Meniscal Tears (STITCH Study)	Number: CTX-CP001
	Version: 1, 4-Sept-2019
	Page: 14 of 15

Pearson Exact method ⁱⁱⁱ, meeting the minimal clinically important differences (MCIDs) from baseline to Days 185 and 365 (MCID185_{IKDC}=6.3, MCID365_{Lysholm} =10.1, MCID365_{IKDC}=16.7) will be presented. There was no MCID for Lysholm at Day 185.

7.10 Analysis of Safety Endpoints:

All safety analyses and summaries will be done using the Safety Population.

The safety analyses will summarize the number (n) and percentages (%) of:

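### The MCID responder rate in SAP 7.9 leaves out subjects whose repair failed and who were withdrawn before the visit, so it tends to overstate response

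*SAP*

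**What the plan says.** SAP 7.4 (Derived Data) defines three flags: IKDC at Day 185 (change above 6.3), IKDC at Day 365 (above 16.7) and Lysholm at Day 365 (above 10.1). The second reads "MCID-IKDC (Day 365) Indicator = 1 if IKDC difference from baseline to Day 365 > 16.7". In all three, any other case is 0, and an absent score is not mentioned.

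SAP 7.9 (Patient Reported Outcomes) is the only place that defines a rate. It presents the number and proportion of subjects "meeting the minimal clinically important differences (MCIDs) from baseline to Days 185 and 365", with an exact Clopper-Pearson interval and a denominator described as "out of total number of subjects providing data". It does not say whether the data must come from that visit, and it names no analysis population for these outcomes.

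SAP 7.3 gives the general rule: "All data will be analyzed as observed cases unless otherwise indicated".

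Two other provisions decide who has a score. Protocol 5.3 states that treatment failures are withdrawn so that they can receive other treatment. SAP 7.2 excludes early withdrawals from the Analysis Population, apart from an exception for closure that is not explained.

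**The concern.** Under these rules a missing score is not always a neutral event. A subject may lack a Day 365 score because a visit was missed, or because the repair failed and the protocol took the subject out of the study. The observed-case denominator treats the two alike and drops both. In the second case the outcome itself causes the missing score, and dropping it favours the procedure.

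The MCID proportion is the only analysis in the SAP that asks whether the gain in patient-reported outcome is large enough to matter to the patient. IKDC and Lysholm are both listed as primary endpoints in SAP 5.1. Protocol 3.2 describes meniscectomy as a failure endpoint of this study, so a responder rate computed without the failed repairs fits poorly with the study's own view of failure. With about 27 subjects, each one moves the rate by roughly 4 percentage points (1/27 = 3.7%).

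**Working it through.** **No figure to reproduce.** The documents give no expected responder rate, no dropout rate and no count of missing scores, and SAP 6.1 states that no formal sample size calculation was made. The one available figure is the number analysed. SAP 6.1 says "it was planned to enroll 30 subjects into the study, and the sample size was accrued" and that "a total of 3 subjects were excluded from all analyses for having met protocol deviations", so N = 30 − 3 = 27.

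**Path of a failed repair through the plan**

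1. The repair fails before Day 365, and Protocol 5.3 withdraws the subject.
2. No Day 365 score is expected, so there is no change from baseline.
3. SAP 7.9 counts only subjects providing data, and the subject leaves the denominator.
4. If the Analysis Population is used, the early-withdrawal exclusion in SAP 7.2 may remove the subject before any flag is computed.

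**Formulas.** Let m be the number of the 27 without a score at the visit, f the number of those m who were reoperated at the index site or withdrawn as failures, and x the number of responders.

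- As written (SAP 7.9, data at that visit): x / (27 − m)
- Failures counted as non-responders, other missing scores left out: x / (27 − m + f)
- Difference: x·f / [(27 − m)(27 − m + f)], which is zero when f = 0

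**Illustration.** Assumed, not from the documents: m = 4, x = 16, f from 0 to 4. Intervals are two-sided 95% Clopper-Pearson.

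| f | As written | Failures as non-responders | Difference (points) |
|---|---|---|---|
| 0 | 16/23 = 69.6% (47.1 to 86.8) | 16/23 = 69.6% (47.1 to 86.8) | 0 |
| 1 | 16/23 = 69.6% | 16/24 = 66.7% (44.7 to 84.4) | 2.9 |
| 2 | 16/23 = 69.6% | 16/25 = 64.0% (42.5 to 82.0) | 5.6 |
| 3 | 16/23 = 69.6% | 16/26 = 61.5% (40.6 to 79.8) | 8.0 |
| 4 | 16/23 = 69.6% | 16/27 = 59.3% (38.8 to 77.6) | 10.3 |

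A second assumed case, m = 5 and x = 15, gives 15/22 = 68.2% (45.1 to 86.1) as written. Counting failures gives 15/23 = 65.2% with one failure, 15/25 = 60.0% with three and 15/27 = 55.6% with five.

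**Effect of the residual 0 in SAP 7.4.** The numerator in SAP 7.9 counts flags equal to 1. Whether an absent score is coded 0 or missing, x does not change, and the denominator is still those providing data. Both codings give x / (27 − m).

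**The case against.** A reader might infer that the plan contradicts itself: SAP 7.4 would make every subject without a score a non-responder, SAP 7.9 would drop the same subject, and there would be two conflicting rates. The documents do not support this. SAP 7.4 defines a subject-level flag and no rate, SAP 7.9 defines the only rate, and that rate is the same under either coding. A figure such as 16/27 with all four missing counted as failures arises only if the flag is averaged over everyone, or if providing data is read as data at any visit. Nor does SAP 7.4 say that an absent score is coded 0. That is an inference from its residual category, and the observed-case default in SAP 7.3 points the other way. What stands is a gap in wording. In SAS, a missing change compared with a cut-off evaluates as not greater, so a literal transcription would produce a 0 without warning.

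A stronger objection is that failures do not vanish from the report. SAP 7.9 gives freedom from reoperation and the proportion reoperated with exact intervals, and SAP 7.6 summarises and lists reasons for withdrawal. The study tests no formal hypothesis, and the MCID proportion is a descriptive addition. All of this is true and limits the consequences. It does not correct the responder rate, because a reader of that rate cannot tell how many failed repairs were left out of it.

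It is also fair to say that how a failure counts is a choice of what to estimate, and that the number of failures among the missing is unknown. The first is a reason for the SAP to state the choice. The second means that the size cannot be fixed from the documents.

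**Conclusion.** The concern holds as an omission with a predictable direction. Followed as written, SAP 7.9 and Protocol 5.3 together remove failed repairs from the MCID denominator, and the rate is too high as a measure of response among treated subjects whenever failures are among the missing. SAP 7.2 may add a second removal, depending on which population is used. The wording of SAP 7.4 is an ambiguity and a programming risk, not a second rate.

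On the assumed counts with two failures among four missing, the overstatement is 5.6 points: 69.6% (47.1 to 86.8) against 64.0% (42.5 to 82.0). The intervals overlap widely. The size rests on four assumptions: 27 subjects entering the analysis, the assumed m, f and x, no failed subject supplying a score at the visit, and the view that a failed repair is a non-response. With f = 0 there is no difference.

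**What to change.** In SAP 7.4, define each of the three flags as:

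- 1 if the change exceeds the cut-off;
- 0 if it does not, or if the subject was reoperated at the index site or withdrawn as a treatment failure before that visit (this takes precedence over any later score);
- missing if the baseline or visit score is absent for any other reason.

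In SAP 7.9:

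- make the denominator the treated subjects with a non-missing flag;
- state that subjects withdrawn as failures are not removed by the early-withdrawal exclusion for this analysis, since otherwise recoding the flag would not bring them back;
- show the number missing at each visit;
- add a sensitivity line with all missing flags set to 0.

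The inputs are already planned: the protocol lists case report forms for reoperation details and for study completion, and Protocol 5.3 asks the investigator to try to record the reason for withdrawal. The cost is SAP wording and a few lines of code, with no new data collection. The downside is a slightly lower headline responder rate if failures occurred.

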1.	List of Abbreviations	4
2.	Introduction.....	4
3.	Study Design	4
4.	Study Objectives.....	6
5.	Study Endpoints.....	6
5.1	Primary Endpoint(s)	6
5.2	Safety Endpoint(s).....	6
6.	Statistical Considerations	7
6.1	Determination of Sample Size.....	7
6.2	Randomization	7
6.3	Interim Analysis.....	7
7.	Statistical Analysis	7
7.1	General	7
7.2	Analysis Populations.....	8
7.3	Handling of Missing, Incomplete and Repeat Data	8
7.4	Derived Data	9
7.5	Baseline Data	10
7.6	Disposition Data.....	11
7.7	Protocol Deviations	12
7.8	Multiplicity	12
7.9	Analysis of Primary Endpoint(s)	12
7.10	Changes in Analysis Methods Specified in the Protocol.....	14
8.	References.....	15

CONFIDENTIAL AND PROPRIETARY

This document contains information that is confidential and proprietary to Smith & Nephew PLC and Smith & Nephew, Inc. and is intended for use only by Smith & Nephew and its manufacturer. It shall not be reproduced or copied in whole or in part, nor shall the contents be disclosed by any means without prior written permission from Smith & Nephew, nor shall anyone make any use of it that is contrary to the expressed or implied wishes of Smith & Nephew

Statistical Analysis Plan	Smith+Nephew
A Prospective, Non-randomized, Multi-Center Investigation of All-suture-based Repair of Horizontal Meniscal Tears (STITCH Study)	Number: CTX-CP001
	Version: 1, 4-Sept-2019
	Page: 4 of 15

1. List of Abbreviations

Abbreviation	Definition
ADL	Activities of Daily Living (KOOS)
IKDC	International Knee Documentation Committee
KOOS	Knee Disability and Osteoarthritic Outcome Score
QOL	Quality of Life (KOOS)
S&N	Smith & Nephew Inc.
SAP	Statistical Analysis Plan
TFL	Tables, Figures, and Listings

2. Introduction

The following Statistical Analysis Plan (SAP) details the statistical considerations, including the data analysis methods, for the Study Protocol CTX-CP001 (14th-Dec-2014). Related documents to this SAP are the Study Protocol, Case Report Form (CRF), and Tables, Figures and Listings (TFL) Templates Shells. The statistical analyses specifications presented herein will thus form the basis of the 2-year final study report.

3. Study Design

The study is an interventional trial designed as a non-randomized, single-arm, open-label study of horizontal repairs of the meniscus tears using commercially available products. The study was designed to enroll 30 subjects at up to 10 investigational sites in the United States.

Table 3.1 shows the planned visit schedule.

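### The IKDC responder cut-off moves from 6.3 at Day 185 to 16.7 at Day 365, so the two proportions are not comparable over time, and withdrawn treatment failures can leave the denominator

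*SAP*

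**What the plan says.** SAP 7.4 defines three responder indicators on change from baseline:

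- IKDC at six months: "MCID-IKDC (Day185) Indicator = 1 if IKDC difference from baseline to Day 185 > 6.3".
- IKDC at one year: "MCID-IKDC (Day 365) Indicator = 1 if IKDC difference from baseline to Day 365 > 16.7".
- Lysholm at one year: "MCID-Lysholm (Day365) Indicator = 1 if Lysholm difference from baseline to Day 365 > 10.1".

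SAP 7.9 repeats the three values. It plans proportions, with Clopper-Pearson intervals, of subjects "meeting the minimal clinically important differences (MCIDs) from baseline to Days 185 and 365", taken "out of total number of subjects providing data". It explains one gap ("There was no MCID for Lysholm at Day 185") but does not mention a responder proportion at Day 730. In the introduction, the SAP states that its specifications "will thus form the basis of the 2-year final study report".

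The continuous scores are treated differently. SAP 7.9 summarises them at every visit and gives confidence intervals and p-values for change from baseline, "i.e. from Study Visit 1 to Day 90, Day 185, Day 365, and Day 730".

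Three other provisions decide who is counted. Protocol 5.3 withdraws subjects considered treatment failures. SAP 7.3 analyses observed cases. SAP 7.2 defines an Analysis Population that leaves out early withdrawals. SAP 7.9 does not say which population the responder proportions use.

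**The concern.** Two IKDC proportions, six months apart, would be reported on the same scale and from the same baseline, but against cut-offs that differ by a factor of 2.65. A reader of the report would naturally take them as a time course. A cohort that held its gain, or improved modestly, could then appear to lose responders between six months and one year. The sections that define and use the thresholds do not warn against this. There is no responder figure at two years to set beside the other two.

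The denominator raises a second problem. Subjects withdrawn as failures supply no later score, so they are not in the Day 365 denominator. The proportion then describes those who stayed and will tend to overstate the result for everyone treated. The two effects act in opposite directions at Day 365, and nothing in the plan makes them cancel.

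**Working it through.** **Inputs from the documents.** IKDC cut-offs of 6.3 and 16.7 (SAP 7.4 and 7.9, which agree). 30 subjects planned and 3 excluded from all analyses (SAP 6.1), so at most 27. The documents state no responder rate and no mean or SD of IKDC change, so there is no planned figure to reproduce.

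**Step 1: without any distribution.** The cut-off rises by 16.7 − 6.3 = 10.4 points, and 16.7 / 6.3 = 2.65. Any subject whose gain is constant, above 6.3 and no more than 16.7, changes from responder to non-responder.

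**Step 2: size for a group (assumed inputs).** Let the gain be normal with the same mean m and SD s at both visits. Then P(gain > t) = 1 − Φ((t − m)/s), and the apparent drop is P(gain > 6.3) − P(gain > 16.7). For m = 20, s = 18:

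- Day 185: 1 − Φ((6.3 − 20)/18) = 77.7%
- Day 365: 1 − Φ((16.7 − 20)/18) = 57.3%
- Drop: 20.4 points, with no change in any patient's status

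Other assumed values (drops computed before rounding):

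| Mean | SD | Above 6.3 | Above 16.7 | Drop (points) |
|---|---|---|---|---|
| 10 | 12 | 62.1% | 28.8% | 33.3 |
| 15 | 15 | 71.9% | 45.5% | 26.4 |
| 20 | 15 | 81.9% | 58.7% | 23.2 |
| 25 | 20 | 82.5% | 66.1% | 16.4 |
| 25 | 22 | 80.2% | 64.7% | 15.5 |
| 30 | 15 | 94.3% | 81.2% | 13.1 |
| 30 | 25 | 82.8% | 70.3% | 12.6 |
| 40 | 20 | 95.4% | 87.8% | 7.6 |
| 40 | 12 | 99.8% | 97.4% | 2.4 |

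For means 20 to 30 and SDs 15 to 25 the range is 12.6 to 23.2 points. For means 15 to 25 and SDs 15 to 22 it is 15.5 to 26.4. Over means 10 to 40 and SDs 12 to 25 it is 2.4 to 33.3. With one common cut-off the drop would be 0.

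**Step 3: improvement needed to stay level.** With s fixed, the proportion is unchanged only if the mean gain rises by the full 10.4 points, for example from 20 to 30.4. If it rises from 20 to 26 with s = 18, the Day 365 proportion is 1 − Φ((16.7 − 26)/18) = 69.7%. This is still below 77.7%, although the cohort improved.

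**Step 4: precision.** With n = 27, m = 20 and s = 20, the expected counts are about 20/27 (Clopper-Pearson 95% CI 53.7% to 88.9%) and 15/27 (35.3% to 74.5%).

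**Step 5: the denominator.** If a fraction f of subjects is withdrawn as failures and a proportion p of the remainder responds, the plan reports p, whereas counting failures as non-responders gives p(1 − f). The overstatement is p × f. With illustrative counts of 5 failures among 27 and 13 responders among the other 22, the plan reports 13/22 = 59.1%, against 13/27 = 48.1%, a difference of 11 points. With no failures the difference is zero.

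**The case against.** The strongest reply is that an MCID may properly depend on follow-up time, and that SAP 7.9 presents separate visit-specific proportions without saying that they will be compared. Durability can be read from the continuous scores. The study tests no formal hypothesis (protocol 4.1, SAP 6.1), the responder proportions are not among the endpoints in SAP 5.1, and the threshold effect makes the one-year result look worse, not better. All of this stands. It limits the importance of the point, but it does not make the two proportions comparable. The References section listed in the SAP contents is not in the text available, so nothing is inferred about the source of 6.3 and 16.7.

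Several stronger readings are tempting but are not supported:

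- A reader might infer that the two-year result is missing. It is not. SAP 7.9 plans mean changes with intervals and p-values to Day 730, and freedom from reoperation at two years.
- A reader might infer a definite loss of about 20 points. That figure needs an assumed mean and SD and an unchanged distribution of gains. A large enough real improvement would show a rise.
- A reader might take the zero-otherwise coding in SAP 7.4 to mean that missing scores count as non-response. The indicator is a function of a difference, which does not exist without a score, and SAP 7.3 and 7.9 both point to observed cases. A clarifying sentence is enough.
- A reader might say that the denominator loses exactly the failures. Protocol 5.3 also allows withdrawal for non-cooperation, investigator judgement and withdrawn consent, and covers loss to follow-up. Failures with scores from before withdrawal still count at those visits.

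An objection to the remedy also has force: using 6.3 after Day 185, 16.7 outside Day 365, or 10.1 at Day 730 takes a threshold outside the visit for which the SAP gives it. Such columns must be labelled descriptive and not called MCID results.

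**Conclusion.** The point holds in this limited form. The Day 185 and Day 365 IKDC responder proportions are not comparable over time. That follows from the definitions alone. Its size is illustrative: about 13 to 23 points for assumed means of 20 to 30 and SDs of 15 to 25, given a normal gain that does not change between visits, and under 10 points for most larger gains examined, such as a mean of 40. Only the responder proportion is absent at Day 730.

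The denominator problem also holds. Following protocol 5.3 with SAP 7.9, or using the Analysis Population, can remove failures and raise the proportion by p × f; the number of failures is not known from the documents. Neither issue affects a formal test. Both affect how a 2-year report would be read, and both are cheap to correct before reporting.

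**What to change.** 1. Keep the visit-specific MCID results as planned. Add descriptive columns for IKDC at both 6.3 and 16.7 at Days 185, 365 and 730, and for Lysholm at 10.1 at Days 365 and 730, all with Clopper-Pearson intervals.
2. Label every threshold used outside its own visit as descriptive, and state that comparisons over time are made only within one threshold.
3. Name the population for the responder proportions: all treated subjects (the Safety Population), not the set that excludes early withdrawals. Without this, scoring failures as non-responders would have little effect, because the Analysis Population has already removed early withdrawals. State how the 3 exclusions in SAP 6.1 bear on this denominator.
4. Set the indicator to missing when the score is missing, except 0 for a subject reoperated at the index site or withdrawn as a treatment failure before that visit. Show the observed-case proportion alongside.

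The scores and thresholds are already in hand, so the cost is a few table columns and a short SAP clarification. The responder rate may become slightly less favourable once failures count against it.

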7. SAFETY MEASUREMENTS

7.1. Definitions

Complication

A complication is any untoward medical occurrence, unfavorable and unintended sign (including clinically significant abnormal laboratory finding), symptom, or condition experienced by the subject and temporally associated with the procedure whether or not considered related to the procedure.

Major Complication

Any complication attributable to the meniscal repair procedure that, in the view of either the Investigator or Sponsor, results in any of the following outcomes:

- Death;
- Life-threatening illness or injury;
- Inpatient hospitalization or prolongation of existing hospitalization;
- Persistent or significant incapacity or substantial disruption of the ability to conduct normal life functions;

- Important medical events that, based upon appropriate medical judgment, require medical or surgical intervention to prevent one of the above outcomes.

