5.2 Safety Endpoint(s)

Safety follow-up includes reporting of a:

Complication

A complication is any untoward medical occurrence, unfavorable and unintended sign (including clinically significant abnormal laboratory finding), symptom, or condition experienced by the subject and temporally associated with the procedure whether or not considered related to the procedure.

Major Complication

Any complication attributable to the meniscal repair procedure that, in the view of either the Investigator or Sponsor, results in any of the following outcomes:

- Death;
- Life-threatening illness or injury;
- Inpatient hospitalization or prolongation of existing hospitalization;

CONFIDENTIAL AND PROPRIETARY

This document contains information that is confidential and proprietary to Smith & Nephew PLC and Smith & Nephew, Inc. and is intended for use only by Smith & Nephew and its manufacturer. It shall not be reproduced or copied in whole or in part, nor shall the contents be disclosed by any means without prior written permission from Smith & Nephew, nor shall anyone make any use of it that is contrary to the expressed or implied wishes of Smith & Nephew

Statistical Analysis Plan	Smith+Nephew
A Prospective, Non-randomized, Multi-Center Investigation of All-suture-based Repair of Horizontal Meniscal Tears (STITCH Study)	Number: CTX-CP001
	Version: 1, 4-Sept-2019
	Page: 7 of 15

- Persistent or significant incapacity or substantial disruption of the ability to conduct normal life functions;
- Important medical events that, based upon appropriate medical judgment, require medical or surgical intervention to prevent one of the above outcomes.

6. Statistical Considerations

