- Individual flags for whether each adverse event was a new complication, a major complication (if answer was yes to at least one of the following: related to a fall or other injury, related to surgical procedure, related to meniscal repair, related to device(s) used, resolved, not resolved/ongoing, and/or death.
- The duration of adverse events defined as:
 - Duration of resolved AE (in day) = End date – start date
 - Duration of unresolved AE (in day) = Date of study completion – start date

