- the incidence according to subjects with at least one new complication,
- the incidence according to subjects with at least one new major complication,
- the incidence according to subjects whose complication was related to fall or injury,
- the incidence according to subjects who had at least one complication possibly, probably, or definitely related to surgical procedure,
- the incidence according to subjects who had at least one complication possibly, probably, or definitely related to meniscal repair, and
- the incidence according to subjects who had at least one complication possibly, probably, or definitely related to device(s) used.

A summary table will be presented that summarizes the complications by code according to subjects who had at least one new complication of a particular code.

In addition, for each complication, the following will be summarized: the relationship to the surgical procedure, the relationship to meniscal repair, the relationship to device(s) used, outcome and duration of the resolved complications and the duration of the complications at study discontinuation.

A listing of all new complications per subject will also be presented, along with duration, major complication status (yes/no), resolution status (resolved or ongoing), and relatedness to surgical procedure, meniscal repair, and device(s) used.

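### As printed, SAP 7.4 makes every complication with a recorded outcome a major complication, contradicting SAP 5.2 and Protocol 7.1

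*SAP*

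**What the plan says.** The Adverse Events part of SAP 7.4 (Derived Data) begins "Individual flags for whether each adverse event was a new complication". It then gives a condition for "a major complication (if answer was yes to at least one of the following: related to a fall or other injury", names relation to the surgical procedure and to the meniscal repair, and ends with "related to device(s) used, resolved, not resolved/ongoing, and/or death". The parenthesis is never closed.

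SAP 5.2 defines the same term differently: "Any complication attributable to the meniscal repair procedure that, in the view of either the Investigator or Sponsor" leads to one of five results. These are death, life-threatening illness or injury, new or prolonged hospital stay, lasting or significant incapacity, or an important event needing intervention to prevent one of those. Protocol 7.1 uses the same definition ("in the view of either the Investigator or Sponsor, results in any of the following outcomes"). Protocol 7.2 has the site record in the source document whether an event is major, and why, separately from relatedness and current status.

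The safety section, SAP 7.10, reports "the incidence according to subjects with at least one new complication" and, as a separate row, "the incidence according to subjects with at least one new major complication". Its per-subject listing shows "major complication status (yes/no), resolution status (resolved or ongoing), and relatedness to surgical procedure, meniscal repair, and device(s) used".

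**The concern.** The section that tells the programmer how to build the flag gives a rule that does not separate major from other complications. An event that has resolved meets it, and so does one that has not. The rule does not require attribution to the repair, it admits events related only to a fall, and of the five serious results it names only death.

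Major complications are one of the items Protocol 9.2 lists for descriptive statistics, and SAP 7.10 gives them their own row and a listing column. If SAP 7.4 is followed, the two incidence rows carry the same number and the listing shows yes for every event with an outcome. Neither output would agree with the SAP's own definition or with the classification the sites made under Protocol 7.2.

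**Working it through.** The documents state no figure for this flag, so there is none to reproduce. The check is of the rule's logic.

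**Inputs.** From SAP 7.4: four relatedness items (fall or injury, procedure, repair, device), each taken as yes or no, and three outcomes (resolved, ongoing, death). SAP 7.10 grades three of the relatedness items as possible, probable or definite; treating any of these grades as yes is an assumption. It does not affect step 1, where the outcome alone is enough. Protocol 7.2 makes current status part of the minimum information, and Protocol 8.4 requires all CRF data to be recorded, so a blank outcome should be an exception.

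**1. Rule as printed, outcome recorded.** Patterns: 2^4 × 3 = 16 × 3 = 48. Each has one of the three outcomes, so at least one listed item is yes. Flagged: 48 of 48.

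**2. Rule as printed, blank outcome allowed.** Patterns: 16 × 4 = 64. The only one not flagged has all four relatedness answers no and a blank outcome. Flagged: 63 of 64.

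**3. Only the two resolution items deleted.** A pattern escapes only if all relatedness answers are no and the outcome is resolved or ongoing, which is 2 patterns. Flagged: 48 − 2 = 46 of 48.

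**4. Definition in SAP 5.2 and Protocol 7.1.** Add a serious-result indicator, which is always yes for death. Each relatedness pattern then has 2 + 2 + 1 = 5 combinations of outcome and seriousness, so 16 × 5 = 80 patterns. Repair-related (8 relatedness patterns) and serious (3 combinations) gives 8 × 3 = 24 major. If relation to the surgical procedure also counts as attribution, 12 × 3 = 36 are major. SAP 7.4 flags all 80.

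These are counts of possible answers, not expected frequencies.

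**5. Direction.** An event that meets the SAP 5.2 definition is attributable to the repair procedure. If that attribution is recorded, SAP 7.4 flags the event too. The printed rule therefore adds events and drops none.

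**6. Effect on the reported row.** The counts below are assumed. The denominator is the planned 30, or 30 − 3 = 27 if the three exclusions in SAP 6.1 also apply to safety. *Reported* is subjects with any complication divided by n; *correct* is subjects meeting SAP 5.2 divided by n.

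| Any / major under 5.2 | n = 30: reported vs correct | n = 27: reported vs correct |
|---|---|---|
| 3 / 0 | 10.0% vs 0% | 11.1% vs 0% |
| 10 / 1 | 33.3% vs 3.3% | 37.0% vs 3.7% |
| 12 / 2 | 40.0% vs 6.7% | 44.4% vs 7.4% |

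The gap is always the number of subjects who had complications but none that was major under SAP 5.2, divided by n. The choice of denominator changes little.

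**The case against.** The best defence is that nobody intended this rule. The sentence announces individual flags, its parenthesis is left open, and its relatedness items follow the order of the separate rows in SAP 7.10. The listing there keeps major status, resolution and relatedness apart. On that reading the text is a list of flags with broken punctuation, SAP 5.2 supplies the definition, and Protocol 7.2 already provides a recorded judgement. The CRF and the table shells, which are not available here, may settle the matter. The output is descriptive, in a single-arm study planned for 30 subjects, and two identical rows would probably be noticed at output review.

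Much of this stands. A drafting slip is likely, a careful programmer might use SAP 5.2 anyway, and the effect on the final tables cannot be confirmed from these documents. The pattern counts show only that the rule does not discriminate.

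It does not cure the text. The at-least-one condition is attached to the major-complication flag; if the items are separate flags, the condition governs nothing and SAP 7.4 gives no criterion for major. No sentence in SAP 7.4 or 7.10 refers back to 5.2 or says that 5.2 prevails. SAP 7.4 is where operational rules such as the MCID indicators are set, and the SAP's Introduction says its specifications form the basis of the final report.

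**Conclusion.** The concern holds. Taken as printed, SAP 7.4 contradicts SAP 5.2 and Protocol 7.1, and it makes the any-complication and major-complication rows of SAP 7.10 coincide whenever outcomes are recorded. That conclusion rests on the wording alone and is firm.

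The size of the error in the final tables is unknown. It depends on complication counts that the documents do not give and on whether the programmer follows the sentence literally. The error would overstate harm, and no primary endpoint, significance test or stopping rule uses the flag. It should be fixed before the safety tables are produced, but it does not threaten the trial's main conclusions.

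**What to change.** Replace the parenthesis in SAP 7.4 with a rule of this kind: *major complication = yes if the event meets the definition in SAP 5.2 and Protocol 7.1, using the classification and reason recorded under Protocol 7.2 and any Sponsor determination.* Then list relation to fall or injury, procedure, repair and device, resolved or ongoing status, and death as separate flags. Deleting only the two resolution items is not enough, because any single relatedness answer would still make an event major.

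The cost is one sentence in the SAP and one check of where the classification is held. Protocol 7.2 places it in the source document, the content of CRF 007 (Complication) is not visible here, and the protocol does not say how a Sponsor determination is recorded. The change sets no new clinical rule; it makes the derivation follow the trial's own definition.
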